### 5.7. Mixed Model for Repeated Measures

These hypotheses will be tested using the 1 Year contrast estimated from a mixed model for repeated measures (MMRM) (Verbeke and Molenberghs 2000). The MMRM will include baseline endpoint value (ODI, NRS or EQ-5D), treatment group, visit, and visit by treatment group interaction. Changes from baseline to Months 1.5, 3, and 6, as well as from baseline to 1 Year are included in the MMRM as a function of the fixed effects. A random site effect will be included to account for the randomization within site. A random site effect is appropriate as we wish to generalize to patients from any site and specifically from sites included in this study. Patients lost-to-follow-up due to reasons related to lack of effectiveness or subsequent to a related AE will utilize baseline observation carried forward imputation of missing values; otherwise, missing values are implicitly imputed while estimating the parameters of the MMRM. MMRM produces unbiased estimates when there is missing follow-up when missing-at-random (MAR) assumption is true (Rubin 1976). The MAR assumption is that the likelihood of missing is statistically independent of the distribution of the unobserved missing outcome conditional on observed data and is most reasonable for missingness not associated with lack of efficacy.

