### 3.2. Sample Size Rationale

The sample size for the study is determined under the following assumptions for the primary efficacy endpoint, which are based on a prior study of ReActiv8, and approximately the MMRM test by its corresponding unadjusted t-test. All else being equal, this is a conservative estimate of power since control for baseline and inclusion of intermediate time points is not accounted for.

- Minimum power of 80%
- Type I error of 5%
- Assumed mean change in Treatment group: 18.2
- Assumed mean change in Control group: 12.2
- Pooled Standard Deviation: 15

Under the above assumptions, a minimum of 204 evaluable patients is required in order to demonstrate superiority of the ReActiv8 treatment. To account for attrition, approximately 230 patients will be enrolled and randomized.

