#### Hypothesis Test

The primary superiority hypothesis is that the mean change in ODI from baseline to 1 Year is more negative (i.e., superior to) for patients treated with ReActiv8 Stimulation Therapy compared to patients treated with OMM. Symbolically, the primary effectiveness hypotheses can be represented as follows:

Ho:  $\delta_T - \delta_C \ge 0$ Ha:  $\delta_T - \delta_C < 0$ 

Where  $\delta_T$  and  $\delta_C$  are the true mean changes in ODI from baseline to 1 Year for ReActiv8 Stimulation Therapy (T) and for patients treated with OMM alone (C), respectively. See section 5.7 for a discussion on Mixed Model Repeated Measures. See discussion in Section 5.8 defining the definition of the primary estimand  $\delta_T - \delta_C$ .

The two-sided p-value for the equality null hypothesis will be reported as well as the two-sided adjusted 95% confidence interval for the difference in mean changes. Superiority will only be claimed if p<0.05 and the mean change is more negative (greater improvement) for the Treatment group compared to the Control group. This is equivalent to specifying a one-sided test at  $\alpha$ =0.025.

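### The primary MMRM fits one baseline slope to all four visits and does not state its within-patient covariance; a baseline-by-visit term and a named covariance are a small, cheap improvement

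*SAP*

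**What the plan says.** SAP 5.7 gives the only full description of the model behind the primary and both secondary tests. Its fixed effects are: "The MMRM will include baseline endpoint value (ODI, NRS or EQ-5D), treatment group, visit, and visit by treatment group interaction". The responses are the changes from baseline at Months 1.5, 3, 6 and 1 Year. On random terms it says: "A random site effect will be included to account for the randomization within site". Treatment may therefore vary by visit, but the baseline effect may not.

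Neither document names a patient-level term, a within-patient covariance structure, a fallback if the model fails to converge, or a degrees-of-freedom method. Protocol 3.1.1.1 and 3.1.2 refer only to an MMRM. SAP 5.8 mentions checking error and random-effect distributions without giving a structure.

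Two properties are claimed for the model. On missing data, SAP 5.7 says: "MMRM produces unbiased estimates when there is missing follow-up when missing-at-random (MAR) assumption is true". On power, SAP 3.2 says of the unadjusted t-test calculation: "this is a conservative estimate of power since control for baseline and inclusion of intermediate time points is not accounted for".

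**The concern.** Change in ODI usually depends on baseline, and that dependence can strengthen over follow-up as responses spread out. A single slope averages the visits, and generalized least squares gives most weight to the least variable one. If that is Month 1.5, the 1 Year contrast is adjusted with a slope that describes Month 1.5, and part of the precision available from baseline is lost.

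The unstated covariance matters for a separate reason. An MMRM uses a patient's earlier visits to inform a missing 1 Year value only through the within-patient covariance. SAP 5.8 relies on this for two groups: devices removed for reasons other than lack of effectiveness, and unexplained loss to follow-up. Different structures can also give different 1 Year standard errors, and SAP 4.1 allows tables to be reviewed before final data lock. The same model feeds the Hochberg comparison (SAP 5.5), the poolability test (4.4) and the subgroup interactions (5.11).

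**Working it through.** **1. The plan's own figure.** Inputs from SAP 3.2: difference 18.2 − 12.2 = 6.0, SD 15, two-sided 5%, power 80%.

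- n per arm = 2 × (1.960 + 0.842)² × 15² / 6² = 98.1, so 99 per arm (198 in total). The t-test version needs 100 per arm (200). The plan's 204 is reproduced to within 3%.
- At 102 per arm, SE = 15 × √(2/102) = 2.100. Power = Φ(6/2.100 − 1.960) = 81.5% (81.1% by the t distribution).
- The allowance for attrition is 1 − 204/230 = 11.3%.

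**2. Formulas for the common slope.** Let b₄ be the true 1 Year slope of change on baseline, b_c the fitted common slope, s the baseline SD and σ the 1 Year residual SD. Up to the factor 2/102, the variance of the 1 Year contrast is:

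- visit-specific slopes: σ²
- common slope: σ² + (b₄ − b_c)² s²
- unadjusted: σ² + b₄² s²

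The common slope is a weighted mean of the four visit slopes, with weights proportional to Σ⁻¹1, where Σ is the within-patient covariance.

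**3. Numbers.** The documents give no visit-specific slopes, SDs or correlations, so those below are assumptions. The ODI entry range of 30 to 60 limits the baseline SD; a uniform spread would give 30/√12 = 8.66.

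| | Mild drift | Moderate drift | Strong drift |
|---|---|---|---|
| Slopes, Month 1.5 to 1 Year | −0.2, −0.3, −0.4, −0.5 | −0.10 rising to −0.45 | 0, −0.1, −0.3, −0.6 |
| SD over visits | 15 throughout | residual, 11 to 14.4 | 9, 11, 13, 15 |
| Correlation | 0.7 at lag 1 | 0.5 to 0.75 | 0.7 at lag 1 |
| Baseline SD | 8 | 8.66 | 8 |
| Weight on Month 1.5 / 1 Year | 37% / 41% | 61% / 19% | 76% / 16% |
| Common slope b_c | −0.36 | −0.19 | −0.11 |
| σ at 1 Year | 14.46 | 14.40 | 14.21 |
| Variance ratio, common to visit-specific | 1.006 | 1.024 | 1.076 |
| Power at N=204, visit-specific → common | 83.7% → 83.1% (simulated) | 84.5% → 83.6% (formula) | 86.3% → 83.7% (simulated) |

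- Moderate case: (0.45 − 0.19)² × 8.66² = 5.07, and 1 + 5.07/14.40² = 1.024. A simulation of 3,000 trials gave 1.025.
- Strong case: σ² = 15² − 0.6² × 8² = 201.96. The added term is (0.60 − 0.11)² × 8² = 15.3 (using unrounded b_c), and 1 + 15.3/201.96 = 1.076. Correlation is taken to fall as 0.7 to the power of the lag.
- If the slope is the same at every visit, the ratio is 1 and nothing is lost.
- At σ = 14.4, a 5% rise in variance takes power from 84.5% to 82.7%, about 1.8 points. The upper end of about 3 points corresponds to the strong case.

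In the moderate case each point of chance baseline imbalance shifts the contrast by 0.26 points, and that imbalance has SD 8.66 × √(2/102) = 1.21. This is the same loss in other units: (0.26 × 1.21)² / 2.016² = 2.4%, where 2.016 = 14.4 × √(2/102). It should not be added to the variance figure.

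**4. Validity with unstructured covariance.** Simulations used 1,500 trials per scenario, N=204 complete or N=230 with 15 to 18% dropout. The common-slope model had bias of at most 0.12 ODI points, type I error of 4.4 to 5.3% and power of 82.1 to 83.7%. The Monte Carlo standard error on a 5% rate is √(0.05 × 0.95/1500) = 0.6 points.

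**5. The conservative-power statement.** From step 2, the common slope beats the unadjusted test whenever |b₄ − b_c| < |b₄|. The moderate case gives an effective SD of 14.4 × √1.024 = 14.57, and the strong case √217.3 = 14.74. Both are below 15. The strong-case margin is small (simulated SE 2.07 against 2.10), and slopes that change sign across visits could remove it.

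**6. Worst-case illustration only: the model coded with no within-patient correlation.**

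- One residual variance is then pooled over visits. With SDs 9, 11, 13, 15 the pooled SD is √[(81 + 121 + 169 + 225)/4] = 12.2. Type I error = 2Φ(−1.96 × 12.2/15) = 11.1% (11.4% simulated). Milder rises, from 10–13 to 15, give 6.5 to 9.6%. With constant SD it is about 5%.
- With MAR dropout concentrated in one arm, bias is 0.9 to 1.2 ODI points at 6 to 10% loss and 1.7 to 2.5 points in the 15 to 18% dropout simulations. With similar dropout in both arms it is 0.06 to 0.18.

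**The case against.** The strongest defence is that the SAP plainly intends an ordinary MMRM. It uses the repeated-measures name, cites a longitudinal mixed-model text and says missing values are implicitly imputed. SAP 3.2 expects a gain from intermediate time points, which presupposes correlated visits. That defence stands. A reader might infer from site being the only named random term that visits within a patient are treated as independent, so that the MAR statement fails and the test is anti-conservative. The documents do not support this, because silence on structure does not specify independence. Under unstructured covariance the MAR property holds. The figures in step 6 also need adverse inputs. The larger bias range uses dropout above the implied 11.3%, and SAP 5.8 sends withdrawals for lack of effectiveness or adverse events to baseline carried forward instead of leaving them to MAR.

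A second tempting reading is that a common slope makes the 1 Year comparison biased or the power claim false. Randomization protects the contrast, and the common slope still beat the unadjusted t-test in the complete-data cases run, so neither follows.

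What survives is that the single baseline slope is what the SAP actually states, that a better model is available at almost no cost, and that the MMRM label does not fix which covariance is used.

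**Conclusion.** The point holds as a modest efficiency loss plus a specification gap. The common slope raises the variance of the 1 Year contrast by about 0 to 5% over most of the ranges tried and by about 8% in the steepest drift simulated, which is about 0 to 3 power points at N=204. It costs nothing if the baseline slope is stable. These figures rest on assumed slopes, SDs and correlations. The required sample size reproduces, and the conservative-power statement is not shown to be wrong. The MAR statement is sound under a standard within-patient covariance, but the SAP should name the covariance on which it depends. Baseline-by-visit does not secure MAR validity; the covariance does.

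**What to change.** In SAP 5.7, write the model for ODI, NRS and EQ-5D as: change = baseline, treatment, visit, treatment-by-visit, baseline-by-visit, with a random site effect and unstructured covariance among the four visits within patient. State Kenward-Roger degrees of freedom and an ordered fallback if the model does not converge. Heterogeneous Toeplitz followed by heterogeneous compound symmetry is one reasonable order; what matters is that the order is fixed before outcome results are seen by arm.

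The cost is three degrees of freedom (four baseline slopes in place of one) and a paragraph of SAP wording. Sample size, visits and data collection do not change.

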### 5.8. Defining the Primary Estimand

Further refinement of primary estimand,  $\delta_T - \delta_C$ , and implications for handling missing data and clinical status measures after relevant 'intercurrent' events are now discussed in the context of FDA Guidance E9(R1). The primary estimand is defined as the *treatment group difference in* (adjusted) mean changes from baseline to 1 Year among patients who start their randomized treatment and continue on that treatment throughout the 1 Year follow-up period.

Reasons for missing after initial treatment initiation for patients with at least one follow-up visit (at Months 1.5, 3 6, and/or 1 Year) will be categorized as:

- Withdrawal due to lack of effectiveness
- Crossover from control to ReActiv8 due to lack of effectiveness
- Withdrawal due to removal of ReActiv8 for reasons other than lack of effectiveness (e.g., to obtain an MRI)
- Withdrawal due to adverse event
- Missing due to loss-to-follow-up with no known reason

Randomized patients who do not initiate a study treatment or do not have any follow-up data through 1 Year will be categorized as:

- Randomized to ReActiv8 but withdrawn prior to implant
- Randomized to ReActiv8 but withdrawn before any follow-up visit
- Randomized to OMM but withdrawn before any follow-up visit

E9(R1) sets up the argument for specifying clinically meaningful estimands as follows:

It remains undisputed that randomization is a cornerstone of controlled clinical trials and that analysis should aim at exploiting the advantages of randomization to the greatest extent possible. However, the question remains whether estimating an effect in accordance with the ITT principle always represents the treatment effect of greatest relevance to regulatory and clinical decision making. The framework outlined in this addendum gives a basis for describing different treatment effects and some points to consider for the design and analysis of trials to give estimates of these treatment effects that are reliable for decision-making.

Relevant comments from E9(R1) include:

- Discontinuation of randomized treatment represents an intercurrent event to be addressed in the precise specification of the trial objective through the estimand. Study withdrawal gives rise to missing data to be addressed in the statistical analysis.
- Switching treatment represents an intercurrent event, and the clinical question of interest in respect to that event should be clear.
- In addition, regarding the distinct consequences of different intercurrent events, events such as discontinuation of treatment, switching between treatments, or use of an additional medication may render the later measurements of the variable irrelevant or difficult to interpret even when they can be collected. Measurements after a subject dies do not exist.
- Hypothetical Strategies: A scenario is envisaged in which the intercurrent event would not occur: the value of the variable to reflect the clinical question of interest is the value that the variable would have taken in the hypothetical scenario defined.

With these E9(R1) considerations in mind, defining of the primary analysis set and handling of missing data and data observed subsequent to a relevant intercurrent events are specified as follows:

- Only patients randomized to ReActiv8 who are implanted with the device and who have at least one follow-up assessment (at Months 1.5, 3, 6, and/or 1 Year) will be included in a Full Analysis Set (FAS) to be used in testing of primary and secondary effectiveness endpoints.
- Only control patients who have at least one follow-up assessment (at Months 1.5, 3, 6, and/or 1 Year) will be included in the FAS.
- Patients who are withdrawn from the study due to lack of effectiveness prior to the primary
  efficacy assessment at 1 Year will have their subsequent clinical status indicators defined
  by baseline values (i.e., baseline observation carried forward or BOCF) for the primary
  and secondary endpoint analyses. A sensitivity analysis will be conducted in which their
  subsequent clinical status indicators are defined by last observation carried forward
  (LOCF). Similar methodology will be employed for analyses after the 1 Year time point.

- Control patients who are withdrawn prior to the 1 Year visit to receive ReActiv8 commercially will have their subsequent clinical status indicators defined by baseline values (i.e., BOCF). A sensitivity analysis will be conducted in which their subsequent clinical status indicators are defined by LOCF. The rationale for employing BOCF in primary analyses is the hypothesis that such patients experience negligible improvement in clinical status and therefore desire what they perceive as a potentially effective treatment, ReActiv8.
- Patients withdrawn from treatment due to an adverse event prior to the primary efficacy assessment at 1 Year will have their subsequent clinical status indicators defined by baseline values (i.e., baseline observation carried forward) for the primary and secondary endpoint analyses. A sensitivity analysis will be conducted in which their subsequent clinical status indicators are defined by last observation carried forward. The rationale for employing BOCF in primary analyses is the hypothesis that patients who experience AE severe enough to be withdrawn from their study treatment cannot benefit from the treatment and so the expected change is zero. Similar methodology will be employed for analyses after the 1 Year time point.
- Patients who have their ReActiv8 removed for reasons other than lack of effectiveness prior to the primary efficacy assessment at 1 Year will have their subsequent clinical status implicitly imputed through the use of the MMRM by assuming MAR for the primary and secondary endpoint analyses.
- Patients in either group who have missing primary or secondary endpoint data due to lossto-follow-up with no known reason will have their subsequent clinical status implicitly imputed through the use of the MMRM by assuming MAR.

Residuals from the models will be evaluated to determine if the distributional assumptions concerning error and random effect distributions of the MMRM are tenable. The primary and secondary endpoints are bounded reducing the risk of extreme outliers. Normalizing transformations may be considered if required for validity of the MMRM. If the distributional assumptions of the MMRM are not tenable and no adequate normalizing transformation can be found, corresponding responder analyses will be performed. Responder definitions will be commonly used thresholds that are typically supported through comparison to MCID. Thus, for ODI, the responder definitions is an improvement in ODI of at least 15 points. For NRS, the responder definition is an improvement in NRS of at least 50%. Even if the parametric assumptions of the MMRM are met, descriptive comparisons between groups will utilize these responder definitions.

### 5.9. Safety Assessment

Reportable adverse events (AEs) are those related to the device, procedure, stimulation or other therapies utilized to treat LBP, and all serious adverse events (SAEs), whether related or not.

All reportable AEs will be documented and reported from the time of informed consent through the end of the study with summary statistics presented for observed rates. No formal statistical hypotheses will be tested in the safety assessment.

### 5.10. Supporting Analyses

The supporting efficacy analyses will include:

- Comparison between the Treatment and Control groups in the of responder rate in ODI at the 1 Year visit, where a change ≥15 points is considered a responder
- Comparison between the Treatment and Control groups in the cumulative proportion of responder rate (a comparison of ranks of the percentage of "responders" across the range of all possible response thresholds) in ODI at the 1 Year visit,
- Comparison between the Treatment and Control groups in the of responder rate in NRS at the 1 Year visit, where a change ≥50% is considered a responder
- Comparison between the Treatment and Control groups in the cumulative proportion of responder rate (a comparison of ranks of the percentage of "responders" across the range of all possible response thresholds) in NRS at the 1 Year visit
- Within group changes in all analyses will also be assessed at the 2 Year visit
- Health economic outcome measures at the 1- and 2 Year visits will be compared to baseline
- Activity monitoring will be collected on a subset of patients and assessed through the 2 Year visit and compared to baseline
- Additional ad hoc analyses may also be conducted.

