## 1.1. Overall Synopsis of the Clinical Study

This study is a prospective, randomized study comparing ReActiv8 Therapy to Optimal Medical Management (OMM), where OMM means the patient has been managed according to available guideline-directed treatments (e.g., medication, physical therapy, injections), and are intending to continue with their existing course of care during the study. OMM will follow physician treatment practices per the guidelines such that it will be individualized to meet the patient needs. A synopsis of the study in tabular form is shown in Table 1.

All patients who satisfy the enrollment criteria are randomized (1:1) to receive either ReActiv8 (Treatment group) or OMM (Control group).

After randomization, those in the Treatment group will be implanted, and then all patients will be followed at the following timepoints post-implant: 1.5 months, 3 months, 6 months, 1 year, 18 months, and 2 years. After the 1-year visit, patients in the Control group may elect to be implanted with the ReActiv8 device and, in addition to the visits noted above, will have follow-up visits at 13.5 months and 15 months. Patients in the Control group who are not implanted with a ReActiv8 device after the 1-year visit will be exited from the study at that time.

The primary efficacy endpoint is a comparison of mean change in Oswestry Disability Index (ODI) at 1 year compared to baseline.

Secondary and tertiary endpoints will be assessed at the 1-year visit compared to baseline, including change in Numerical Rating Scale (NRS) Pain score, a composite of change in ODI and change in NRS Pain score, change in EQ-5D Quality of Life, Percent Pain Relief, Subject Global Impression of Change (SGIC), and Treatment Satisfaction.

Related adverse events (AEs) and all serious adverse events (SAEs) will be reported from enrollment through study exit.

Study Purpose	To compare the effectiveness of ReActiv8 to OMM for the treatment of intractable chronic low back pain (CLBP).		
Indications for Use	The ReActiv8 System is indicated for bilateral stimulation of the L2 medial branch of the dorsal ramus as it crosses the L3 transverse process as an aid in the management of intractable chronic low back pain associated with multifidus muscle dysfunction, as evidenced by imaging or physiological testing in adults who have failed therapy including pain medications and physical therapy and are not candidates for spine surgery.		
Study Device	ReActiv8 System		

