Additional Supporting Analyses	
 
Comparison between Treatment and Control in the of responder rate in ODI at 1 year, where a change ≥15 points is considered a responder
 
Comparison between Treatment and Control in the cumulative proportion of responder rate in ODI at 1 year
 
Comparison between Treatment and Control in the of responder rate in NRS at 1 year, where a change ≥50% is considered a responder
 
Comparison between Treatment and Control in the cumulative proportion of responder rate in NRS at 1 year, where a change ≥50% is considered a responder
 
Comparison between Treatment and Control in the cumulative proportion of responder rate in NRS at 1 year
 
Within group changes in all analyses will be assessed at 2 years
 
Cost-effectiveness assessment including:         
 
Change in work status, work-days missed and ability to do their work at 1 and 2 years compared to baseline
 
Health care utilization (office visits, hospital visits, emergency room visits, and other therapies such as physical therapy) at 1 and 2 years compared to baseline
 
 
 
Activity monitoring, including the number of steps and amount of sleep, will be collected on a subset of patients and assessed through 2 years compared to baseline
 
Additional ad hoc analyses may also be conducted
 
		

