### 3.1.5. Supporting Analyses

The supporting efficacy analyses will include:

- Comparison between the Treatment and Control groups in the of responder rate in ODI at the 1-year visit, where a change ≥15 points is considered a responder
- Comparison between the Treatment and Control groups in the cumulative proportion of responder rate in ODI at the 1-year visit
- Comparison between the Treatment and Control groups in the of responder rate in NRS at the 1-year visit, where a change ≥50% is considered a responder
- Comparison between the Treatment and Control groups in the cumulative proportion of responder rate in NRS at the 1-year visit
- Within group changes in all analyses will also be assessed at the 2-year visit

- Endpoints will be further analyzed by baseline EQ-5D index score
- Health economic outcome measures at the 1- and 2-year visits will be compared to baseline
- Activity monitoring will be collected on a subset of patients and assessed through the 2-year visit and compared to baseline
- Additional ad hoc analyses may also be conducted

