#### 3.1.6. Health Economics

Health economic outcome measures to be recorded will include:

- Work status, work-days missed and ability to do their work the year prior to baseline, and at the 1- and 2-year visits
- Health care utilization (office visits, hospital visits, emergency room visits, and other therapies such as physical therapy) the year prior to baseline and at the 1- and 2-year visits

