## 3.2. Study Visits and Data Collection Schedule

The study visit schedule is provided in Table 3. The study visit schedule will vary slightly between the groups to account for the Treatment group being implanted after the randomization visit. For the Treatment group, visit timing for all visits will be based on Activation. For the Control group visit timing through the 1-year visit will be based on Randomization. After those in the Control group are implanted, the timing of the remaining visits will be based on the Activation visit.

Visit	Treatment	Control
Informed consent, baseline	$\checkmark$	✓
Randomization (Approx. 14 days post baseline)	$\checkmark$	✓
ReActiv8 implant (Approx. 14 days post randomization)	$\checkmark$	
Activation (Approx. 14 days post implant)	$\checkmark$	
1.5-month (45 ± 14 days)	$\checkmark$	$\checkmark$
3-month (90 ± 30 days)	$\checkmark$	$\checkmark$
6-month (180 ± 30 days)	$\checkmark$	$\checkmark$
1-year (365 ± 60 days)	$\checkmark$	$\checkmark$
ReActiv8 implant (within 60 days of the 1-year visit)		$\checkmark$
Activation (Approx. 14 days post implant)		$\checkmark$
13.5-month (410 ± 14 days)		$\checkmark$
15-month (450 ± 30 days)		$\checkmark$
18-month (540 ± 30 days)	$\checkmark$	$\checkmark$
2-year (730 ± 60 days)	$\checkmark$	$\checkmark$

Table 3: Visit S	chedule with	Recommended	Visit Windows
	Sheadle with	Reconnicitaca	

A summary of the data collection schedule is shown for the Treatment group in Table 4 and for the Control group in Table 5.

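### The health-economic measures are specified only as change from baseline; a 1-year Treatment-versus-Control comparison and a follow-up period that includes the implant should be written in

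*SAP*

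**What the plan says.** Three places describe the analysis, and all use baseline as the reference.

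- Protocol 1.1 (synopsis table, additional supporting analyses) puts two items under a cost-effectiveness heading. The work item is "Change in work status, work-days missed and ability to do their work at 1 and 2 years compared to baseline". The utilization item covers office, hospital and emergency visits and "other therapies such as physical therapy) at 1 and 2 years compared to baseline".
- Protocol 3.1.5: "Health economic outcome measures at the 1- and 2-year visits will be compared to baseline".
- SAP 5.10: "Health economic outcome measures at the 1- and 2 Year visits will be compared to baseline".

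Protocol 3.1.6 and SAP 5.10.1 list what is recorded. Work measures, for example, are taken for "the year prior to baseline, and at the 1- and 2-year visits", and utilization is handled in the same way. The period that the 1- and 2-year forms look back over is not given.

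Other bullets in the SAP 5.10 list do name the arms, for example "Comparison between the Treatment and Control groups in the of responder rate in ODI at the 1 Year visit".

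On timing, Protocol 3.2 says "For the Treatment group, visit timing for all visits will be based on Activation", whereas Control visits up to 1 year run from Randomization. Protocol Tables 4 and 5 show the utilization and work forms at baseline, 1 year and 2 years in both arms.

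**The concern.** Cost-effectiveness is a question about one strategy against another. A change from baseline within an arm answers a different question: how that arm's patients fared compared with their own previous year. In a randomised trial with an OMM arm completing the same forms, the comparison that isolates the device is available at 1 year but is not named.

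If the line is applied as a simple pre-post analysis, a fall in utilization or missed work in the Treatment group could be read as economic benefit even if OMM patients showed the same fall. If the 1-year form also asks about the last 12 months, the surgical episode and recovery would drop out of the Treatment group's follow-up. These are costs that only that arm incurs during the randomised year.

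**Working it through.** **No plan figure to reproduce.** Neither document gives a mean, SD, cost or sample size for the health-economic measures. The stated minimum of 204 evaluable patients concerns ODI only.

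**Step 1: what each contrast estimates.** Let B be the mean change that would occur under continued OMM and D the added effect of the device strategy.

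- Treatment, change from baseline: B + D
- Control, change from baseline: B
- Treatment minus Control: (B + D) − B = D

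A comparison with baseline in the Treatment group is off from D by exactly B. Pooling the arms 1:1 would give B + D/2, which does not isolate D either. B for work or utilization is not in the documents, and its sign is not known, so the error can be described but not sized.

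**Step 2: is D estimable from data already planned?** At 1 year, yes: both arms have the two forms at baseline and at 1 year (Protocol Tables 4 and 5). At 2 years, no: Control patients are either implanted after the 1-year visit or exited (Protocol 3, SAP 3), so no randomised OMM group remains.

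**Step 3: the follow-up period.** Nominal days from baseline, from Protocol Table 3 (randomization about 14 days after baseline, implant about 14 days later, activation about 14 days later):

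| Event | Treatment | Control |
|---|---|---|
| Randomization | 14 | 14 |
| Implant | 14 + 14 = 28 | – |
| Activation | 28 + 14 = 42 | – |
| 1-year visit | 42 + 365 = 407 | 14 + 365 = 379 |

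There are three possible look-backs at the 1-year visit:

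- *Previous 12 months.* Treatment starts at 407 − 365 = day 42, so the implant at day 28 and the two weeks of recovery are outside it. Control starts at 379 − 365 = day 14, which is Randomization.
- *Since baseline.* Treatment covers 407 days (407/365 = 1.115, 11.5% longer than the baseline year) and Control 379 days (379/365 = 1.038, 3.8% longer).
- *Since Randomization.* Treatment covers 407 − 14 = 393 days and Control 365. The implant is counted, but the lengths differ by 28 days, so rates per patient-time are needed.

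These are nominal values. The 1-year window is ±60 days, and Protocol 5 treats windows as guidance, so individual periods will vary.

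**The case against.** The strongest reply is that the contrast is unspecified rather than excluded. Protocol 1.1 describes even the primary endpoint as a 1-year change relative to baseline without naming the arms in that sentence, yet it is tested between arms. Where SAP 5.10 means a within-group analysis, for the 2-year changes, it says so. A reader might infer that the plan commits to a within-group analysis and rules out a between-arm one; the text does not go that far. What remains is that neighbouring bullets name the arms and this one does not. The allowance for further ad hoc analyses would also leave contrast, period and adjustment to be chosen after the data are seen.

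Second, this is a supporting assessment, not a study objective. It has no hypothesis and no alpha, and the SAP does not use the term cost-effectiveness. That is correct and limits the weight of the point.

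Third, the case report forms are not part of these documents and may state a recall period. The omission of the implant is therefore conditional. Implant details are recorded separately (Protocol 5.3), so the procedure itself could be added back.

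Fourth, a reader might take the sample-size assumptions (ODI improvements of 18.2 and 12.2) and infer that about two thirds of any saving is background change. The documents do not support this. Those are ODI figures from a prior sham-controlled study, and nothing links them to utilization or missed work. Entry criteria select on pain and disability scores, not on health care use.

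**Conclusion.** The point holds as a gap in a supporting analysis. The plan names only a comparison with baseline for measures that the protocol presents as a cost-effectiveness assessment, and that comparison cannot separate a device effect from background change. The size of the resulting error is unknown, because the documents contain no work or utilization figures.

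The timing problem is conditional. With a 12-month look-back and nominal visits, the Treatment period starts at day 42 and misses the implant at about day 28; with another recall period it may not.

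It would be going too far to say that a trial objective fails, that the implant is certainly left out, or that a QALY analysis is owed: neither document promises one. Primary and secondary endpoints are tested between arms and are unaffected.

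**What to change.** In SAP 5.10 and 5.10.1, and Protocol 3.1.5 and 3.1.6:

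1. Make the 1-year health-economic analysis a Treatment-minus-Control comparison of each work and utilization measure, adjusted for the same measure in the year before baseline.
2. State a follow-up period that starts at Randomization in both arms, so that the implant episode is counted, and use rates per patient-time where lengths differ.
3. If the form records only 12-month totals, add the implant episode from the procedure records. Those records will not supply work-days missed during recovery, so that gap should be stated or the recall period clarified on the form.
4. Label changes from baseline, and all 2-year results, as descriptive, because no randomised OMM comparator remains after 1 year.

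The cost is wording in two documents, one more table and possibly a clarified recall period. No new visits or questionnaires are needed. The Treatment result may look less favourable once the implant episode is counted.
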